13.1.2 Side Effects / Tolerability

The hypothesis that hydroxyzine reduces the incidence of nausea, one of the most common side effects of varenicline, will be evaluated by comparison to the benchmark of 30% (20% above placebo rate of 10%) observed in clinical trials of varenicline.³⁶ Initially, 25 participants will be recruited and then the possibility of recruiting 25 more (total N=50) depending on an interim analysis, as follows:

- If 0-3 participants out of 25 (12% or less) report nausea, we would conclude the treatment is highly promising at the interim stage and go directly to an RCT (Branch 1).
- If 4-6 participants (out of 25) report the side effect, then the treatment will be deemed sufficiently promising to recruit an additional 25 participants (Branch 2). If 10 or less of the total 50 report the side effect of nausea (20% or less), a follow-up RCT would be warranted; otherwise the treatment would be deemed unpromising.
- If 7 or more out of 25 (28% or more) report the side effect of nausea in the interim analysis, then we would conclude it is futile to continue the pilot and the study would be terminated (Branch 3).

The frequency of treatment-emergent side effects (i.e., those that begin or worsen after the initiation of treatment) will be tabulated. Due to the problem of Type II error posed by significance testing numerous side effect outcomes (especially if corrections are imposed for multiple comparisons), descriptive statistical methods will instead be used, supplemented by calculation of confidence intervals and p-values as a flagging device to highlight differences worthy of further attention.³⁷ Hypothesis testing will be conducted for only two outcomes: 1) proportion of participants that withdraw from the study due to side effects; 2) overall adherence (i.e., proportion of scheduled doses taken) assessed by daily medication diaries and returned capsules.

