4.4 DISCONTINUATION OF PARTICIPANTS FROM STUDY

Discontinued participants will include both participants who withdraw from the study (participant's decision) or participants who are discontinued from the study (following Investigator's decision). A participant can only be discontinued from the study after enrollment. Participants that are not enrolled are considered screen failures.

Participants will be informed that they are free to withdraw from the study at any time. Participants should be questioned for the reason of premature withdrawal from the study, although they are not obliged to disclose it.

Participants discontinued from the study cannot re-enter the study.

4.4.1 Participants must be discontinued from the study for any of the following reasons:

- No-show to appointments and unable to reschedule within the visit window.
- Withdrawal of informed consent.
- Any adverse effect or condition that would jeopardize continued safe study participation.
- Pregnancy test is positive.
- Discontinuation is considered to be in the best interest for the participant or for other participants participating to the study, as judged by the Investigator or designee.

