9.3.2 Varenicline

Varenicline is one of the most widely used prescription medications for smoking cessation. Common adverse events associated with varenicline include nausea, insomnia, abnormal dreams, headaches, and nasopharyngitis. ¹⁹ The most common adverse reaction reported is nausea, with 30-40% of participants in randomized control trials reporting mild to moderate levels of nausea. ³³ Discontinuation/drop-out rates of nearly 10% have been noted during clinical trials due to these adverse effects. ³⁴ In addition to the potential drug-specific side effects noted, any medication may trigger a serious allergic reaction and may cause shock, seizures (convulsions, epilepsy, "fits"), loss of consciousness, tingling, swelling of the face, lips, tongue, throat and/or vocal cords, difficulty breathing, asthma, wheezing, rash, hives, itching, and possibly death.

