9.4 PROTECTION AGAINST RISKS

Participants will be screened medically and monitored throughout the study. Participants will be instructed to report any side effects to study staff, who will communicate these reports immediately to the medical staff. The most appropriate course of action will be determined, which may include options for dose reduction or termination of treatment. Participants whose treatment is terminated will be encouraged to remain in the study for assessment of outcomes and to receive continuing social support for quitting smoking. Participants will, however, be reminded that they have the option to withdraw from the study at any time. Participants will also be given the 24-hour emergency contact number in the event that side effects or adverse events occur between sessions.

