11.2 COLLECTION OF SAFETY EVENTS FROM PARTICIPANTS

Information recorded when collecting AEs will include: thorough description of the AE, seriousness assessment, start and stop dates (if known), circumstances leading up to the event, clinical elements such as clinical course, specific vital signs and test results that may explain the pathophysiology of the event, as well as alternative explanations to its occurrence, the action taken with the investigation

product/procedures due to the AE, the participant's disposition in the study after the occurrence of the AE and the final outcome of the AE (if known).

Any exacerbation/worsening or increased frequency of an AE or pre-existing condition shall be evaluated and recorded.

AEs should be collected using questionnaires and face-to-face interviews with the participant. The Adverse Effects Form is a targeted checklist-based questionnaire with items selected to detect common side effects from product use. This questionnaire also contains an open-ended section for participants to record any additional effects.

Whenever a medically meaningful diagnosis is available to comprise a set of reported signs and/or symptoms, it should be preferentially provided as the AE or SAE term, rather than the individual signs and/or symptoms. Otherwise, each one of those signs and/or symptoms should be reported separately as event terms.

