13.1 EFFICACY AND TOLERABILITY

13.1.1 Abstinence Outcomes

Abstinence at each time point will be defined by a self-report of no cigarette smoking (not even a puff) since the prior session, confirmed by an expired air CO reading of less than 5 ppm. The primary

abstinence outcome will be abstinence during weeks 8-11 post-quit date. An intent-to-treat approach will be taken in which any participants lost to follow-up after the point of randomization, or who have relapsed prior to the end of treatment (week 11 post-quit) will be counted as non-abstinent (in accordance with recent guidelines from the FDA). A secondary smoking abstinence outcome will be 7day point abstinence at 6 months post-quit, for participants who have not relapsed prior to the end of treatment. The main goal of the 6-month follow-up is to assess the persistence of therapeutic effects for those who do achieve end-of-treatment abstinence. This information will be helpful in determining the treatment duration in future Phase 3 clinical trials. The main hypothesis to be evaluated in this pilot study is that the incidence of varenicline-associated side effects, specifically nausea, will be diminished by co-administration of hydroxyzine, relative to historical benchmarks (see below). A one-tailed test of abstinence will be conducted, however, comparing the proportion of participants abstinent during weeks 8-11 to the historical benchmark of 45% abstinence, to provide evidence that abstinence is not significantly lower than it would be with varenicline alone. There is no reason to expect that abstinence rate would be reduced by hydroxyzine; if anything, abstinence would be expected to be enhanced by amelioration of varenicline-associated side effects and by potential effects of H1 antagonists to reduce nicotine reward.35

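### The withdrawal-due-to-side-effects test in section 13.1.2 has no null value or direction, and its wording undercounts tolerability failures

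*Combined protocol and SAP*

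**What the plan says.** Section 13.1.2 describes most side effects without formal testing and then makes an exception: "Hypothesis testing will be conducted for only two outcomes: 1) proportion of participants that withdraw from the study due to side effects". The other exception is overall adherence. No null value, direction, significance level or denominator follows for either. By contrast, nausea is compared with 30% in the same section, and section 13.1.1 tests abstinence one-tailed by reference "to the historical benchmark of 45% abstinence".

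Three other places bear on what the withdrawal outcome counts.

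- Section 4.4 divides those who leave into "participants who withdraw from the study (participant's decision) or participants who are discontinued from the study", the latter on the investigator's decision. Section 4.4.1 makes discontinuation mandatory for "Any adverse effect or condition that would jeopardize continued safe study participation". Participants who withdraw are asked why, "although they are not obliged to disclose it".
- Section 9.4 allows dose reduction or termination of treatment for side effects, and adds: "Participants whose treatment is terminated will be encouraged to remain in the study for assessment of outcomes".
- Section 9.3.2 gives the only related rate: "Discontinuation/drop-out rates of nearly 10% have been noted during clinical trials due to these adverse effects". It stands in the risk section and is not linked to the test in 13.1.2.

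**The concern.** A single-arm proportion can be tested only against a stated value in a stated direction. Without both, the null and the side of the test could be chosen after open-label data have been seen, for one of the only two tolerability tests the plan kept.

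The second problem is what is counted. A participant whose side effects end treatment can take three routes: leave by their own choice, be discontinued by the investigator, or stop the drugs and remain for follow-up. The words in 13.1.2 clearly cover only the first. The plan requires the second in some cases and encourages the third, so the proportion leans towards a favourable result. If it were then set against the rate of nearly 10% in 9.3.2, a narrower outcome would be compared with what is described as a broader one.

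At stake is how well the pilot describes the tolerability of the combination to those who plan the randomised trial of about 200 participants. The go/no-go decision itself is not at stake.

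**Working it through.** **1. The plan's own figures.** Section 13.1.3 gives none for the withdrawal test. It gives operating characteristics for the nausea rule only: advance at 3 or fewer of 25, stop at 7 or more of 25, otherwise advance at 10 or fewer of 50. With X1 the count in the first 25 and X2 the count in the second 25:

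P(advance) = P(X1 ≤ 3) + Σ over x = 4, 5, 6 of P(X1 = x) × P(X2 ≤ 10 − x)

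| True nausea rate | Branches 1 / 2 / 3, exact | Stated | P(advance), exact | Stated |
|---|---|---|---|---|
| 30% | 3.3 / 30.7 / 65.9% | 3 / 31 / 66% | 8.6% | 9% |
| 15% | 47.1 / 45.9 / 7.0% | 47 / 46 / 7% | 86.1% | 86% |
| 10% | 76.4 / 22.7 / 0.9% | 77 / 22 / 1% | 98.5% | 98% |

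These agree within rounding and simulation error. No withdrawal term enters them.

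**2. What the withdrawal wording counts.**

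| Route after a side effect | Where provided for | Counted by 13.1.2? |
|---|---|---|
| Participant chooses to leave | 4.4 | Yes, if the reason is given |
| Investigator discontinues | 4.4, 4.4.1, 11.8 | Not on a literal reading of 4.4 |
| Treatment ends, participant stays | 9.4 | No |

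**3. How much an undercount could matter (illustration only).** Assumed, because the plan gives no value: null p0 = 10% (the figure in 9.3.2), one-sided 0.05, test for excess. The share m of failures that is missed is also an assumption, shown as a range. N = 25 or 50 comes from 13.1.2.

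- Cut-off c: the smallest r with P(X ≥ r | N, p0) ≤ 0.05.
- Counted rate = true rate × (1 − m).
- Detection = P(X ≥ c | N, counted rate).

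N = 50: P(X ≥ 9 | 0.10) = 0.058 and P(X ≥ 10 | 0.10) = 0.025, so c = 10. N = 25: P(X ≥ 5 | 0.10) = 0.098 and P(X ≥ 6 | 0.10) = 0.033, so c = 6. For a true rate of 20%:

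| Missed | Counted rate | Detection, N=50 | Detection, N=25 |
|---|---|---|---|
| 0% | 20% | 55.6% | 38.3% |
| 10% | 18% | 41.2% | 28.8% |
| 25% | 15% | 20.9% | 16.2% |

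**4. Sensitivity to the assumed null and level (N = 50, true 20%).** Detection with 0 / 10 / 25% missed:

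- null 5%, c = 6: 95.2 / 90.7 / 78.1%
- null 8%, c = 8: 81.0 / 70.0 / 48.1%
- null 12%, c = 11: 41.6 / 28.1 / 12.0%
- null 10% at one-sided 0.10, c = 9: 69.3 / 55.8 / 33.2%

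The loss has the same direction throughout, but its size depends on choices the plan does not make.

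**5. The opposite direction (fewer withdrawals than 10%).** At N = 50, P(X ≤ 1 | 0.10) = 0.034 and P(X ≤ 2 | 0.10) = 0.112, so the cut-off is 1 or fewer. If the true rate is 10% and 25% of failures are missed, the counted rate is 7.5%, and the chance of declaring an improvement rises from 3.4% to 10.3%. At N = 25, even 0 of 25 gives 0.9^25 = 0.072, so no reduction could be shown at 0.05. The direction therefore determines whether the test can succeed at all at the interim size.

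**The case against.** The strongest reply is that these failures are not lost. Adherence, the other tested outcome, falls directly when someone stops treatment but stays. Treatment-emergent side effects are tabulated with intervals and flagging p-values. Section 11.2 calls for a record of the action taken with the "product/procedures due to the AE, the participant's disposition in the study after the occurrence of the AE", and section 11.8 follows up discontinuations for an adverse event. All of that stands, and it is why the point is minor. The cover is partial, though. A mean share of doses taken does not show how many people stopped or why, and adherence has no comparator either.

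It can also be said that the terms in section 4.4 overlap: those who withdraw are a subset of discontinued participants, and withdrawal of consent is listed in 4.4.1 among the reasons for discontinuation. That stands too. For investigator discontinuations, the documents show only that they can be left out. For participants who remain under 9.4 no such doubt exists, since they have not left the study.

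Low power is a separate problem that better counting does not cure: at N = 25 the illustrative test finds a true 20% rate only 38.3% of the time with full capture.

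Three stronger readings are tempting and not supported.

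- A reader might infer that the planned test drops from 55.6% to 2.5% detection if half of the failures are missed. The plan contains no such test, and nothing in it supports a half. Halving 20% gives exactly the assumed null of 10%, so 2.5% is simply the size of the illustrative test.
- A reader might infer that the power figures in 13.1.3 pass for overall tolerability. That section says it concerns the incidence of nausea.
- A reader might infer that the decision to advance is compromised. It depends on nausea alone.

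**Conclusion.** The point holds as a minor one. The withdrawal test cannot be run as specified, and its outcome is biased low as a measure of tolerability failure. That bias follows from the wording for participants who stop treatment and stay, and is possible for investigator discontinuations. The outcome also does not match the discontinuation/drop-out rate in 9.3.2. Whether that rate covers all adverse effects or nausea only cannot be settled from the documents, because the phrase follows a sentence about nausea.

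The size of the undercount is unknown. The detection figures rest on an assumed null, level, direction and missed share, and describe an illustrative test. N = 50 is reached only through Branch 2, which by 13.1.3 happens in 31%, 46% or 22% of trials at true nausea rates of 30%, 15% or 10%.

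**What to change.** In section 13.1.2:

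- Define the outcome as participants who left the study (by their own or the investigator's decision) or permanently stopped varenicline or hydroxyzine because of side effects. Also show the two drugs separately. Dose reductions under 5.4 and 6.3 would not count.
- Use all participants dispensed study drug as the denominator.
- Repeat the result with leavers who give no reason counted as side-effect failures.
- Report the count with an exact 95% confidence interval. Test only if a benchmark and direction are fixed beforehand, for example one-sided for excess above 10%, and only if the source cited in 9.3.2 is confirmed to cover all adverse effects. A varenicline-alone rate contains no hydroxyzine stops, so the separate display is needed to read any excess.

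The cost is protocol wording. The data are already called for in 11.2, and section 4.4 already asks leavers for their reason. The downsides are a less favourable tolerability figure, attribution of reasons in an open-label study, and wide intervals: 5 of 25 (20%) gives 6.8 to 40.7%, and 10 of 50 (20%) gives 10.0 to 33.7%. Section 13.1.3 and the nausea rule need no change.

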3.1.4 Stepwise Evaluation Algorithm

3.2 STUDY PLAN

After obtaining informed consent, adult smokers will be enrolled into the study. There will be an observational period of at least five days to obtain baseline data on use of combustible cigarettes and stress/anxiety and nausea symptoms.

Varenicline Dose = 0.5 mg QPM x 3 days, then 0.5 mg BID x 4 days, then 1.0 mg BID x 11 weeks Hydroxyzine Dose = 50 mg QPM x 3 days, then 25 mg QAM + 50 mg QPM

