5.3 Dosage

- First 3 days of treatment: PM two 25 mg tablet orally.
- Starting on the fourth day of treatment and continuing until the EOS: AM one 25 mg tablet orally; PM two 25 mg tablets orally.
- Dosing will be adjusted based on reported side effects.

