5.4 Dose Adjustment Procedures

Dose adjustments for hydroxyzine will be performed by licensed medical providers based on adverse effects reported by participants (e.g. daytime sedation...stop the AM dose of hydroxyzine, difficulty waking in the am...decrease nighttime dose of hydroxyzine). Participants will be contacted with a follow-up call by Research Medical Staff within 72 hours of any dose adjustment.

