6.3 Dose Adjustment Procedures

Dose adjustments for varenicline will be performed by licensed medical providers based on adverse effects reported by participants (e.g. insomnia, abnormal dreams, mood disturbances, anxiety...decrease dose to 0.5 mg twice a day for moderate to severe side effects). Participants will be contacted with a follow-up call by Research Medical Staff within 72 hours of any dose adjustment.

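### Neither of the two side-effect outcomes reserved for testing in section 13.1.2 need register a participant whose dose was reduced or stopped for side effects

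*Combined protocol and SAP*

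**What the plan says.** Section 13.1.2 compares nausea with a 30% benchmark and treats other side effects descriptively, with confidence intervals and p-values used as flags. It then makes two exceptions: "Hypothesis testing will be conducted for only two outcomes: 1) proportion of participants that withdraw from the study due to side effects", and second, "overall adherence (i.e., proportion of scheduled doses taken) assessed by daily medication diaries and returned capsules". It gives no benchmark, test or alpha for adherence, and does not say whether *scheduled* means the regimen as assigned or as later amended.

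Elsewhere the protocol describes dose changes made because of side effects:

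- **Hydroxyzine.** The Dosage section (5.3) itself states "Dosing will be adjusted based on reported side effects". Section 5.4 gives the examples "daytime sedation...stop the AM dose of hydroxyzine, difficulty waking in the am...decrease nighttime dose of hydroxyzine".
- **Varenicline.** Section 6.3 gives "decrease dose to 0.5 mg twice a day for moderate to severe side effects" as its example.
- **Either drug.** Section 9.4 describes responses to side effects "which may include options for dose reduction or termination of treatment", and adds: "Participants whose treatment is terminated will be encouraged to remain in the study for assessment of outcomes".

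The daily SMS survey (8.8.2, Appendix 14) asks one yes/no question for the morning and one for the evening, covering both study drugs together. It records neither which drug was taken nor how much.

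**The concern.** The pilot is meant to show whether the combination is tolerable enough to justify a randomized trial of about 200 participants. One foreseeable response to intolerance is a dose cut or a dropped dose. That is not withdrawal from the study, and it need not lower the proportion of scheduled doses taken. The two tested figures can therefore both look perfect in a participant who did not tolerate the assigned regimen, and no planned outcome counts dose changes.

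This also affects how the nausea result is read. Low nausea at full varenicline dose and low nausea after varenicline has been halved are different evidence, and the planned summaries would not separate them.

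**Working it through.** **The plan's own figures.** The only operating characteristics stated are for the nausea rule (13.1.3). An exact two-stage binomial calculation (25 participants: success at 3 or fewer, continue at 4 to 6, stop at 7 or more; then success at 10 or fewer of 50) gives:

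- At 30% nausea: branches of 3.3%, 30.7% and 65.9%, and Type I error 8.6% (stated 9%).
- At 15% nausea: branches of 47.1%, 45.9% and 7.0%, and power 86.1% (stated 86%).

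These reproduce. No corresponding figure exists for adherence, so the rest is arithmetic on the regimen.

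**Assigned regimen over 84 days.** Section 3.2 gives "Varenicline Dose = 0.5 mg QPM x 3 days, then 0.5 mg BID x 4 days, then 1.0 mg BID x 11 weeks"; hydroxyzine is in 3.2 and 5.3.

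- Dosing occasions per drug: 3 + 81 × 2 = 165, or 330 for both drugs.
- Varenicline: 3 × 0.5 + 4 × 1 + 77 × 2 = 159.5 mg.
- Hydroxyzine: 3 × 2 + 81 × 3 = 249 tablets of 25 mg, or 6,225 mg.

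**Assumed example.** The dose changes from day 15, leaving 70 days, and every prescribed dose is taken afterwards. The documents give neither the date nor the later intake.

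| Change for side effects | Score on amended schedule | Score on assigned schedule | Assigned amount taken |
|---|---|---|---|
| Varenicline to 0.5 mg twice daily | 100% | 165/165 = 100% | (159.5 − 70)/159.5 = 56% of mg |
| AM hydroxyzine stopped | 100% | (165 − 70)/165 = 58% of hydroxyzine occasions; (330 − 70)/330 = 79% of both drugs' occasions | (249 − 70)/249 = 72% of hydroxyzine tablets |
| PM hydroxyzine cut to one tablet (assumed size of cut) | 100% | 100% by occasion; 72% by tablet count | 179/249 = 72% of hydroxyzine tablets |
| All treatment stopped, participant stays | 100% | (3 + 11 × 2)/165 = 25/165 = 15% | not calculated |

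**Range for a change after day 7 to after day 42.**

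- Varenicline mg taken: (159.5 − 77)/159.5 = 52% to (159.5 − 42)/159.5 = 74%.
- All treatment stopped, assigned occasions taken: 11/165 = 7% to 81/165 = 49%.

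**Group illustration.** Suppose 10% to 20% of participants have AM hydroxyzine stopped from day 15. Each loses 70/330 = 21.2 points of adherence across both drugs against the assigned schedule, and none against the amended one. The means then differ by 0.10 × 21.2 = 2.1 to 0.20 × 21.2 = 4.2 points. The 10% to 20% is an assumption. The documents put drowsiness on hydroxyzine at 10% or more (5.1, 9.3.1), but an incidence of drowsiness is not a rate of stopped doses.

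**The diary.** A participant whose AM hydroxyzine has been stopped still takes morning varenicline and can truthfully answer yes to the morning question. Only returned product could show the change, and only if it is compared with the assigned regimen.

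**The case against.** **The decision to proceed does not use adherence.** A reader might infer that the combination could advance to the larger trial on flattering adherence. The documents do not support that: every branch in 3.1 and 13.1.2 depends on the nausea count alone. This objection stands in full.

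**Intolerance is recorded elsewhere.** Treatment-emergent side effects are tabulated. The Adverse Effects Form asks about drowsiness, fatigue and nausea at each visit from V2. Section 11.2 records the action taken for each event. Section 4.4.1 requires discontinuation for an adverse effect that would jeopardize safe participation, so the withdrawal outcome will capture some severe cases. It would be wrong to say intolerance goes unseen. What remains is that no planned summary reports how many participants had a dose changed.

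**Returned tablets can reveal some changes.** The evening hydroxyzine dose is two tablets, so a cut to one can appear in the return count if the assigned schedule is the reference. A reader might conclude that every reduction is hidden on any reading. That is secure only for varenicline, where the number of doses is unchanged. For stopped doses, the 100% score depends on the amended-schedule reading.

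**The size is easily overstated.** Hydroxyzine occasions alone give 70/165 = 42.4 points per affected participant, or about 4 to 8 points at a 10% to 20% stop rate. The outcome is overall adherence, and across both drugs the figure is about half that.

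**Adherence to the prescribed schedule is a legitimate measure.** Dose adjustment is built into this regimen, and mg taken over mg assigned answers a different question: it mixes a participant's missed doses with a provider's decisions. This stands, and argues against replacing the tested outcome.

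**Conclusion.** The concern holds in limited form. The two tested side-effect outcomes can both be perfect in a participant whose treatment was reduced or stopped for side effects.

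- For halved varenicline this follows from counting doses, whatever *scheduled* means: 56% of assigned mg is taken in the day-15 example, and 52% to 74% over the range examined.
- For stopped doses, including all treatment stopped while the participant remains in the study, it follows only on the amended-schedule reading, which the plan leaves open.

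The dates and full intake afterwards are assumptions. The documents give no expected rate of dose changes, so the group effect cannot be fixed; 2 to 4 points of overall adherence is an illustration. The nausea rule and its error rates are untouched. The gap limits what the pilot can report about tolerability at the assigned doses, and is best closed before results are seen.

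**What to change.** In section 13.1.2:

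1. Beside the withdrawal proportion, report the proportion of participants with any provider-directed reduction or stop of either drug for side effects, including treatment stopped while remaining in the study, with an exact 95% confidence interval.
2. Keep adherence as a compliance measure, and state whether its denominator is the assigned or the amended schedule.
3. Give mg taken over mg assigned for each drug as a descriptive supplement, not as a replacement for the tested outcome.

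The data are already collected: dispensing and return records (5.5.1, 6.4.1), unused-product logs (5.5.3, 6.4.3) and the action-taken information for adverse events (11.2). The cost is a few lines of wording and one extra table. The reported tolerability may look somewhat less favourable. No dosing rule changes.
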